#### 8.4. AEs of Study Procedures

Events that may be regarded as expected complications associated with the investigations are shown in the table below.

**Table 5.** Known complications associated with study procedures conducted in this study.

Procedure	Known complications
Spirometry	Cough, breathlessness
Blood Sampling	Fainting, vasovagal events, bruising or swelling at site of venepuncture
Bronchodilators	Tachycardia, tremor, cough, nausea, headache
Methacholine test	Headaches, throat irritation, light headedness, chest tightness, breathlessness cough, wheezing
Sputum Induction	Nausea, vomiting, salty taste, wheeze, breathlessness, cough

### 9. Statistical Plan

#### 9.1. Sample Size Estimation

It is assumed that 60 subjects will be screened to randomize 30 subjects, and 15 will be randomized to complete each treatment arm in 1:1 ratio. This is a proof-of-concept study investigating the effectiveness of mepolizumab on objective cough rates in patients with

eosinophilic asthma or NAEB. As such, no formal power calculation can be currently performed. The sample size is therefore based on previous similar pilot studies using cough monitoring as an endpoint (36, 37).

With 15 patients per arm, this study will have 80% power with an alpha of 5% to detect an estimated 20% greater reduction in 24hr cough frequency compared with the placebo arm, assuming a log standard deviation of 0.60. A clinically relevant reduction in cough frequency of 20% was established following a recent phase 3 studies of gefapixant in refractory chronic cough which showed a 20% reduction over placebo as significant (38). The data from this study will be used to estimate the sample size required for any future multi-centre studies.

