### **5. Study Design**

#### **5.1. Design**

This is a 9-visit randomized, double-blind, placebo controlled, parallel group study evaluating the effectiveness of 4 doses of mepolizumab for the treatment of refractory chronic cough in patients with eosinophilic airways disease (Figure 1). We plan to complete 15 subjects in each arm of the clinical trial. The duration of intervention will be 12 weeks, during which

subjects will receive 4 doses at days 0, 28, 56 and 84. The effects of mepolizumab on objective cough frequency will be tested at week 14, 2 weeks following the last dose of mepolizumab/placebo.

**Figure 1.** Study flow diagram detailing the study visits and procedures per visit per subject following enrolment.

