### **5.12. Washout Period**

This study does not have a washout period because this is a parallel group study design.

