### **5.13. Blinding and Randomization**

Subjects will be assigned to one of the two possible treatment arms generated by a computer-generated randomisation schedule prepared by McMaster University, with a ratio of 1:1, mepolizumab or placebo. As there is a known imbalance in the prevalence and cough rates, the study will include sex as a randomisation factor. This will mitigate the possibility of the intervention being confounded by sex differences in the 2 arms of the study. Blinded study drug supplies will be provided in sequentially numbered identical syringes in accordance with the randomisation schedule and dispensed by a pharmacist who shall not be delegated any other role in the study. Subjects, investigators, research staff (with the exception of the pharmacist) and the sponsor will be masked to the treatment sequence assignment. A sealed code-break envelope for each subject containing details of the treatment allocated will be kept in a locked safe at the study site.

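### The stated 80% power for a 20% greater reduction does not follow from 15 per arm and a log SD of 0.60; those inputs give about 17%

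*Combined protocol and SAP*

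**What the plan says.** Section 9.1 (Sample Size Estimation) first declines to give a calculation: "As such, no formal power calculation can be currently performed". It bases the size on earlier pilot studies that used cough monitoring. The next paragraph then gives a calculation: "With 15 patients per arm, this study will have 80% power with an alpha of 5% to detect an estimated 20% greater reduction" in 24-hour cough frequency against placebo, "assuming a log standard deviation of 0.60". It treats 20% as the clinically relevant effect, citing a 20% reduction over placebo in phase 3 studies of another drug.

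The number of patients is consistent throughout. Section 5.1 says "We plan to complete 15 subjects in each arm of the clinical trial", and section 5.13 allocates patients "with a ratio of 1:1, mepolizumab or placebo". Section 5.12 confirms two independent groups. Under section 9.2.1 cough frequency is log transformed and summarised as geometric means. Under section 9.2.2 the primary analysis is a GEE model with baseline cough frequency as a covariate.

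The document does not give the log base, the sidedness of the 5%, or whether 0.60 is the SD of the week-14 value, of the change from baseline, or of the residual after baseline adjustment. It assumes neither a baseline correlation nor a placebo response.

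**The concern.** A 20% difference is small beside a log SD of 0.60. With 15 per arm the standard error of the difference in log means is about 0.22, as large as the effect to be detected. An effect of one standard error cannot carry 80% power at the 5% level, so the sentence looked wrong on sight.

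The power statement tells ethics reviewers, the funder and readers what the trial can conclude about its primary endpoint. As written, it promises a one-in-five chance of missing an effect the section calls clinically relevant. If the true chance of missing it is about five in six, a non-significant result says almost nothing about a 20% effect. A reader relying on the stated power could reasonably take it as evidence against one. The section also contradicts itself by ruling out a formal calculation and then reporting one.

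**Working it through.** **Inputs.** From section 9.1: n = 15 per arm, alpha 5%, effect 20% greater reduction than placebo, log SD 0.60. From sections 5.12 and 5.13: two parallel arms, 1:1. From section 9.2.1: analysis on the log scale. Assumed for the main calculation because not stated: natural log, two-sided test, and 0.60 as the SD of the quantity analysed.

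**Attempt to reproduce the 80%.**
- Effect on the log scale: −ln(0.80) = 0.2231.
- Standardised effect: 0.2231 / 0.60 = 0.372.
- Standard error: 0.60 × √(2/15) = 0.2191.
- Noncentrality: 0.2231 / 0.2191 = 1.019, against a critical t (28 df) of 2.048.
- Power from the noncentral t: **16.6%** (normal approximation 17.3%). The plan's 80% is not reproduced.

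**What 15 per arm can detect.** With 28 df, 80% power needs a standardised effect of 1.060. The log difference is 1.060 × 0.60 = 0.636, a ratio of exp(−0.636) = 0.53, or a **47% greater reduction** (46% by the normal approximation).

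**What a 20% effect needs.** By the normal approximation, n = 2 × [(1.960 + 0.842) × 0.60 / 0.2231]² = 113.5, so 114 per arm; by the noncentral t, **115 per arm**. To keep 15 per arm, the analysis SD would have to be 0.2231 / 1.060 = 0.21, about a third of the stated 0.60.

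**Precision.** An observed ratio of 0.80 would have a 95% CI of 0.80 × exp(±2.048 × 0.2191), which is 0.51 to 1.25. Significance requires a log difference of at least 2.048 × 0.2191 = 0.449, an observed reduction of about 36%. A result exactly on the 20% target could not be significant.

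**Other readings of log base and sidedness, with SD 0.60.**

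| Reading | Power, two-sided | Power, one-sided |
|---|---|---|
| Natural log | 16.6% | 25.8% |
| log2 (0.322 / 0.60 = 0.537) | 29.5% | 41.6% |
| log10 (0.0969 / 0.60 = 0.162) | 7.1% | 11.3% |

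**If 0.60 is the SD before baseline adjustment** (natural log, two-sided; residual SD = 0.60 × √(1 − r²); the small loss of degrees of freedom is ignored).

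| Baseline correlation r | Residual SD | Power for 20% | Reduction with 80% power | n per arm for 20% |
|---|---|---|---|---|
| 0.5 | 0.520 | 20.6% | 42% | 87 |
| 0.7 | 0.428 | 28.1% | 36.5% | 59 |
| 0.8 | 0.360 | 37.4% | 32% | 42 |
| 0.9 | 0.262 | 61.6% | 24% | 23 |

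On this reading 80% needs r = √(1 − (0.2106/0.60)²) = 0.94.

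**If 20% means percentage points on top of the placebo fall.** The ratio is (1 − p − 0.20)/(1 − p), where p is the placebo reduction. Power is 32% at p = 30%, 61% at 50%, 79% at 57% and 81% at 58%. It therefore reaches 80% only if placebo itself falls by 57% to 58%.

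**The case against.** The strongest objection is that 17% is itself conditional. It takes 0.60 as the SD of the analysed quantity, on natural logs, with a two-sided test, and section 9.1 states none of these. The planned analysis adjusts for baseline, so if 0.60 is the unadjusted SD the real power is higher: 62% at a correlation of 0.9. Combined assumptions go further. With log2 and a correlation of 0.85, power is 77% two-sided and 86% one-sided; two-sided log2 reaches 80% at a correlation a little above 0.86. So it cannot be said that no reading gives 80%. This stands, and the 16.6%, the 115 per arm and the interval of 0.51 to 1.25 should all be read as unadjusted figures. It does not rescue the sentence, because the document states none of the assumptions needed.

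A second objection is that the size rests on precedent from pilot studies and the trial is labelled proof of concept, so the power sentence decides nothing. This is right about the sample size, and no increase is asked for. It does not excuse a wrong figure attached to the primary endpoint.

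Third, one might fear that the error would pass into the later multi-centre trial. The text does not support that: section 9.1 says the data collected here will be used to size it. Nor does the protocol say how a non-significant result will be interpreted. The misreading described above is a risk, not a stated plan.

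**Conclusion.** The concern holds. The stated 80% does not follow from the stated inputs. With natural logs, a two-sided 5% test and 0.60 as the analysis SD, power for a 20% greater reduction is 16.6%, and 80% power is available only for a reduction of about 47%. Changing log base or sidedness alone leaves power between 7% and 42%. Baseline adjustment with correlations from 0.5 to 0.9 gives 21% to 62%. The readings that reach 80% are a natural-log correlation of about 0.94, log2 combined with a high correlation, or percentage points added to a placebo fall of 57% to 58%. None is stated, and the last sits badly with the section's own benchmark of a reduction over placebo. All these figures assume that 15 per arm complete, as planned; the 30 to be randomised include no allowance for dropout. The sentence must be corrected, because it misstates what the trial can show on its primary endpoint.

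**What to change.** 1. State what 0.60 is (log base; SD of the week-14 value, of the change, or of the baseline-adjusted residual), where it comes from, and whether the 5% is two-sided. If a baseline correlation or a placebo response was assumed, give it and its source.
2. Recalculate on that basis and replace the power sentence. If 0.60 is the natural-log SD of the quantity analysed, suitable wording would be: *With 15 per arm, a natural-log SD of 0.60 and a two-sided 5% test, the study has 80% power for a 47% greater reduction than placebo; power for a 20% greater reduction is about 17%. The study is intended for estimation, results will be given with 95% confidence intervals, and a non-significant result will not be taken as absence of a 20% effect.* If 0.60 is the unadjusted SD, give the baseline-adjusted figures with the assumed correlation (for example, 36.5% detectable and 28% power at a correlation of 0.7). If 0.60 is already the residual SD, do not apply the adjustment again.
3. Remove the contradiction by deleting the statement that no formal calculation can be performed, or by confining it to the choice of sample size.

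The cost is a change of protocol wording and a less favourable stated figure. No patients, visits or procedures are added, and 15 per arm can stay on the pilot-study rationale.

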## 9.2. Statistical Analysis

### 9.2.1. General Considerations, Assumptions, and Definitions

This study will generate data of demographics, LCQ scores, modified Borg scores for sensations and cough, methacholine (PC20), blood eosinophils, sputum eosinophil, total and activated mature eosinophils in sputum and blood. These continuous variables will be presented and analysed as either mean (S.D), median (IQR) or geometric mean (geometric S.D). It is generally assumed that cough frequency data will not be normally distributed, and hence cough frequency data will be log transformed and shown as geometric mean (geometric S.D). Statistical significance will be set at  $p<0.05$ .

For the purposes of analysis, the populations for analyses will be defined as:

1. Full analysis set (FAS): consists of all subjects randomized to a treatment arm, who received at least one dose of investigational product irrespective of their protocol adherence and performed at least one period of 24-hr cough monitoring before and one after treatment.
2. Per Protocol Set (PPS): consists of all patients in who did not have any major protocol deviations, and provided cough frequency recording at baseline, 4 weeks and 8 weeks after treatment.

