## 5.2. Duration of Study

The total length of a subject's participation in the trial is up to 16 weeks;

- Up to 2 weeks screening period
- 14-week intervention period

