##### ***Visit 4: Week 4 Administration of Mepolizumab/Placebo (2nd Injection)***

All subjects will undergo Ontario Covid-19 Assessment Tool and Information Letter prior to study visit. Subjects will return to the clinical research facility 4 weeks following Visit 3. Subjects will undergo blood sampling and complete the Leicester Cough Questionnaire, the modified Borg Scale, and the Cough Severity VAS. Urine will be collected in WOCBP to screen for pregnancy. The second injection of mepolizumab/placebo will be administered in the clinical research facility by a study physician. The subject will be observed for a minimum of 1 hour for the appearance of any acute drug reactions.

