### **C. Objective Cough Monitoring:**

Participants will be asked to wear an ambulatory cough monitor (VitaloJAK™, Vitalograph, UK) for 24 hours, 3 times during the study: Visits 2, 5 and 8. This involves attaching an air microphone to the lapel of the clothing and a chest sensor on the sternum. The VitaloJAK cough recorder is worn around the waist of the subject. Subjects will wear the cough monitor for a continuous 24 hours and return the following day for the procedures for the next visit. Subjects will be informed not to have a shower during this period to prevent the air microphone and chest sensor being damaged by water.

The VitaloJAK cough monitor is a non-invasive, battery operated, and custom-built validated recording device and microphone intended to acquire, record and store ambulatory cough sounds from participants for 24 hours. Briefly, this consists of a digital data logger recording sounds at a sample rate of 8 kHz, with 16-bit resolution and in Waveform Audio File format, which is a commonly used uncompressed sound file format. Recordings will be transferred to a personal computer; silences and background noise will be removed by using validated, custom-written software, and cough sounds will be counted by using an audio editing package. The number of coughs will be expressed as coughs per hour and added up to give a cough count for a 24-hour period, awake cough frequency, and night-time cough frequency.

The cough monitor is an audio recording device and will record all sound including conversations. The cough monitor microphones capture speech in the local vicinity in addition to cough sounds. Therefore, it is possible that despite processing of the cough recording by customised software, some of the participant’s conversations are also

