*iv) The Cough Severity Visual Analogue Scale (0-100mm)* is a single item that assesses a patient's severity of cough over a recall period of 1 week using a 0 to 100mm horizontal visual analogue scale (VAS). Participants will rate their severity of cough on the scale which has a minimum value of 0 equalling "no cough" and a maximum value of 100 equalling "worst cough". A higher score indicates greater cough severity.

**Table 1.** Visit and procedure schedule.

Visit	1	2	3	4	5	6	7	8	9
Study Day	1	$13 \pm 7^*$	$14 \pm 3^{\dagger}$	$42 \pm 3^{\dagger}$	$70 \pm 3^{\dagger}$	$71 \pm 3^{\dagger}$	$99 \pm 3^{\dagger}$	$113 \pm 7^{\dagger}$	$114 \pm 3^{\dagger}$
Post-Randomization	-14	-1	0	28	56	57	84	98	99
Week	-2		0	4	8		12	14	
Procedure									
Ontario Covid-19 Assessment Tool	X	X	X	X	X	X	X	X	X
Informed Consent	X								
Medical History	X								
Adverse Events		X	X	X	X	X	X	X	X
Prior and Con Meds		X	X	X	X	X	X	X	X
Examination	X								
Vital Signs	X	X	X	X	X	X	X	X	X

Urine B-HCG ¥	X		X	X	X		X		
Spirometry	X		X			X			X
Cough Monitoring		X			X			X	
Methacholine PC 20	X								X
Induced Sputum	X #		X			X			X
Blood Sampling	X		X	X		X	X		X
LCQ	X		X	X		X	X		X
mBorg Scale	X		X	X		X	X		X
Cough Severity VAS	X		X	X		X	X		X
Mepolizumab/Placebo			X	X	X		X		

\* May be shortened to 7 days or extended to 21 days depending on availability of sputum cell counting to confirm eligibility of sputum eosinophilia >2%.

†Flexibility provided to allow visits cough monitoring on Friday and subsequent visit on Monday.

¥ Urine pregnancy test will be done for women of childbearing potential (WOCBP) prior to administration of IP.

#Sputum induction at visit 1 could be repeated after 24-48 hours if insufficient sample at visit 1.

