#### *9.2.2. Primary Endpoint*

The primary endpoint in this study will be the change from baseline in 24-hour cough frequency (geometric mean) after 14 weeks of intervention over placebo (day 98, visit 8) adjusted for baseline cough frequency (day 13, visit 2). The primary efficacy endpoint will be analysed using a generalised estimating equation modelling (GEE) analysis including the baseline cough frequency as a co-variate. Both FAS and PPS populations will be analysed.

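### The Per Protocol Set requires a week-4 cough recording that is never made and omits the week-14 primary recording, so its primary analysis cannot be run as written

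*Combined protocol and SAP*

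**What the plan says.** Section 9.2.1 defines two analysis sets. The FAS takes everyone randomised who had at least one dose, regardless of adherence, and has at least one cough recording before and one after treatment. The PPS takes patients with no major protocol deviation who "provided cough frequency recording at baseline, 4 weeks and 8 weeks after treatment".

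Section 9.2.2 places the primary endpoint at week 14 (day 98, Visit 8), adjusted for baseline cough frequency, and states: "Both FAS and PPS populations will be analysed". Section 5.1 agrees on the timing: the effect on cough frequency "will be tested at week 14, 2 weeks following the last dose of mepolizumab/placebo".

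Section 5.11 C has the monitor worn "for 24 hours, 3 times during the study: Visits 2, 5 and 8", and Table 1 marks the same three visits. For Visit 4, the week-4 visit, Section 5.10.2 says: "Subjects will undergo blood sampling and complete the Leicester Cough Questionnaire, the modified Borg Scale, and the Cough Severity VAS". A urine pregnancy test where applicable and the second injection complete that visit. Neither the text nor Table 1 puts a cough monitor there.

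**The concern.** There are two separate faults in one sentence. The PPS demands a recording that the schedule does not produce, and it does not demand the recording that is the primary endpoint. The first empties the set. The second means that striking out the 4-week condition does not repair it.

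The PPS is the only planned set that takes adherence into account. Before it can be analysed, someone must choose a replacement rule, and several are plausible: week 14 only, weeks 8 and 14, or week 8 only. Where a recording is missing, these do not select the same people. With 15 planned per arm, each person is 1/15, about 7%, of an arm.

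Section 9.4 requires an amendment and disclosure for any change to the statistical plan, but it sets no date relative to unblinding. If the rule is chosen with the data in view, the PPS loses its value as a check on the FAS result.

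**Working it through.** The plan gives no figure to reproduce here. The check sets the PPS time points against the recording schedule.

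**Inputs.** All days are from the post-randomization row of Table 1, where the first dose is day 0.
- Doses: days 0, 28, 56 and 84 (Section 5.1).
- Cough recordings: day −1 (Visit 2), day 56 (Visit 5) and day 98 (Visit 8).
- Visit windows: ±3 days for Visit 5 and ±7 days for Visit 8. Table 1 attaches these to study days; I assume they carry over to the post-randomization row.
- Final visit: day 99 (Visit 9).

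**Step 1. Weeks from each dose to each post-baseline recording**, computed as (recording day − dose day)/7:

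| Counted from | Visit 5 (day 56) | Visit 8 (day 98) | Both 4 and 8 weeks? |
|---|---|---|---|
| Dose 1, day 0 | 8 | 14 | No |
| Dose 2, day 28 | 4 | 10 | No |
| Dose 3, day 56 | 0 | 6 | No |
| Dose 4, day 84 | −4 (before dose) | 2 | No |

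No single reference dose gives recordings at both 4 and 8 weeks.

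**Step 2. Can the windows close the gap on the two natural readings?**
- From the first dose, the rule needs days 0 + 28 = 28 and 0 + 56 = 56. Day 56 is Visit 5. The earliest Visit 5 is 56 − 3 = day 53, which is 53 − 28 = 25 days after day 28. One of the two required recordings exists.
- From the last dose, the rule needs days 84 + 28 = 112 and 84 + 56 = 140. The latest Visit 8 is 98 + 7 = day 105, 7 days short of day 112. Day 140 is 140 − 99 = 41 days after the final visit and lies outside the "14-week intervention period" of Section 5.2. Neither required recording exists.

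**Step 3. Size of the set.** At most two of the three required recordings (baseline, 4 weeks, 8 weeks) can exist for anyone. The number who can qualify is 0 of 30.

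**Step 4. What if only the 4-week condition is removed?** The rule becomes baseline plus week 8. A participant meets it once the Visit 5 recording is returned at Visit 6 (day 57). From then to the primary recording is 98 − 57 = 41 days, or 41/98 = 42% of the time from first dose. That is a calendar fraction, not a loss rate. Section 5.14 supplies one way to leave in that interval, withdrawal for an upper respiratory tract infection. Such a person would satisfy the recording rule with no week-14 value. No week-14 result is shifted by this, since there is none to shift; what changes is who is counted in the set.

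The documents give no loss rate, and failed recordings are to be repeated within 24–48 hours (Section 5.10.2, Visits 3, 6 and 9), so I put no count on those affected.

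**The case against.** The strongest reply is that this is a wording slip with an evident meaning. Sections 7.2, 9.2.2 and 9.2.3 consistently work with weeks 8 and 14, the FAS primary analysis is intact, no data are lost, and Section 9.4 already requires any change to go through an amendment. All of that is true, and it keeps the point well short of threatening the trial. It does not make the written rule usable, and the intent is not unique: the rule could be meant to require week 14 alone or weeks 8 and 14 together.

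A second reply is that Visit 5 is both 8 weeks after dose 1 and 4 weeks after dose 2. That reading makes one recording satisfy two listed time points by switching the reference dose mid-sentence, and it still does not require week 14.

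A third is that the FAS can also hold people without a week-14 value, since it needs only one recording after treatment, and that a GEE fitted to both visits could use a week-8-only participant. The first part is correct: the FAS escapes the 4-week error but shares this feature. Whether the primary model includes week 8 is not clear from Sections 9.2.2 and 9.2.3. For a set defined by adherence, leaving out the primary assessment is harder to defend than it is for the FAS.

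Finally, a missed Visit 8 recording might be treated as a major deviation. The plan does not define major deviations, so this cannot be relied on, and it could not supply a week-4 recording in any case.

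**Conclusion.** The concern holds. As written, the PPS is empty (0 of 30), and the PPS analysis of the primary endpoint promised in Section 9.2.2 cannot be run. The 8-week recording is scheduled; the faults are the 4-week condition and the absence of week 14.

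The conclusion rests on reading the recording times as a joint requirement counted from one reference dose, and on the schedule in Section 5.11 C and Table 1, which agree with each other. The effect is limited to the PPS, and no bias in the FAS estimate follows from it. It should be corrected, and the timing of the correction matters more than its difficulty.

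**What to change.** By protocol amendment before unblinding, replace the PPS definition in Section 9.2.1 with:

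> FAS participants with no major protocol deviation and valid 24-hour cough recordings at baseline (Visit 2) and week 14 (Visit 8); for week-8 analyses, a valid recording at week 8 (Visit 5) is also required.

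This uses only scheduled recordings and guarantees a week-14 value for every PPS member. Requiring all three recordings for every analysis would also work and keeps the present rule's form of baseline plus two later recordings. Its price is that anyone who missed only week 8 would be dropped from the primary PPS analysis. Either is acceptable if fixed in advance. The same amendment should say what makes a recording valid and which deviations count as major, since both decide membership.

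The cost is a short amendment: to the REB for information if classed as administrative, or for approval if classed as substantial (Section 13.6). No visit, recording or data collection changes.
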